#### 8.2.4 General statistical considerations

The study is explorative in nature. An analysis of the percent of radioactive parent compound present in blood over time will be performed. Other endpoints will be presented using descriptive statistics.

In general, all data collected will be presented with summary statistics and given in subject data listings. Summary statistics will include at least number of subjects, mean, standard deviation, median, minimum and maximum for continuous data, and frequency and percentage for categorical data. Tables with summary statistics will be divided by group and visit where applicable. Subject data listings will be sorted by treatment, subject and timing of assessments.

For PK assessments, geometric means and CVs will also be presented, where appropriate.

Details of the planned histopathological analysis and the PSMA immunochemistry procedure are given in a separate Histopathology and Immunohistochemistry Manual prepared for this study. The detailed results of such analysis will not be entered into the eCRF, and will be reported separately for each Cohort A subject in a Histopathology and Immunohistochemistry Report to be prepared by the study pathologist and to be included as an Appendix in the Clinical Study Report. The histopathology and immunohistochemistry analysis results that are to be entered into the eCRF are detailed below in section 8.2.6.

#### 8.2.5 Demographic and baseline characteristics

The demographic and baseline characteristics of the subjects will be presented using descriptive summary statistics.

#### 8.2.6 Analysis of efficacy variables

In subjects with PCa, the lesion(s) detected on the PET images will be visually evaluated by the on-site investigator. A semi-quantitative analysis, using standardised uptake values (SUV), will be derived. SUV is a ratio of tissue radioactivity concentration and administered dose of radioactivity divided by body weight:

- SUV = activity (Bq/g)/[injected radioactivity (Bq))/body weight (g)]
- SUVmax is the maximum standardized uptake value.
- SUVmean is the mean standardized uptake value.
- SUVR is a ratio of SUV in a detected lesion and SUV of a reference tissue, such as blood.

The variables will be presented using summary statistics.

Analysis, using SUV, will be used to compare lesions seen on the PET images with lesions from histopathology results, where available. This assessment of which lesion detected on the PET images matches the lesion for which histopathology results are available will be made by the on-site investigator. As far as possible, exploratory comparisons will be made regarding:

- Gleason Scores and degree of uptake of F-rhPSMA-7.3 in primary prostate lesions
- Historical Gleason Score, PSA, PSA kinetics or other biomarkers and degree of uptake of F-rhPSMA-7.3 in metastatic lesions.

Kinetic modelling of the dynamic imaging data in patients will be used to determine the optimal imaging protocol for future studies.

The detailed results of the histopathology and immunohistochemistry analysis of the prostate specimens of the Cohort A subjects will not be entered into the eCRF, but will be reported separately for each Cohort A subject in a Histopathology and Immunohistochemistry Report to be prepared by the study pathologist and to be included as an Appendix in the Clinical Study Report. The immunohistochemistry analysis results that are to be entered into the eCRF include the following:

- Number of carcinoma lesions and their diameter
- Gleason grade/score
  - Primary, secondary and tertiary if applicable

Overall and for each separate carcinoma lesion separately

- Perineural invasion (yes/no)
- Extraprostatic extension (yes/no)
- T-class (pTNM)
- Surgical margin positivity (yes/no, location)
- Seminal vesicle invasion (yes/no)
- Lymph node status (# of metastatic/benign lymph nodes reported for each location with dissected lymph nodes)

Gleason grade will be assigned to all lesions (excluding possible lymph node metastases) as combinations of primary, secondary, and tertiary Gleason grade.

The immunohistochemical staining results will be reported and entered into the eCRF according to the visual intensity of carcinoma cells as follows: score 0 (negative staining), 1 (low intensity), 2 (moderate intensity), and 3 (high intensity). For each carcinoma lesion, the overall (average) staining intensity and the highest (maximum) intensity will be reported based on the expected localization of PSMA at the apical plasma membrane and in the cytoplasm. In the case of intrafocal heterogeneity, the percentage of differently stained tumour cells will be estimated and reported (e.g. 50 % moderate, 50 % high).

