## 2.4 Secondary endpoints

The secondary endpoints of the study are:

1. Dosimetry estimates and cumulated activity exposure by source region and the entire body including analysis of activity in whole blood, plasma and excreted urine in healthy volunteers.
2. Uptake of  $^{18}\text{F}$ -rhPSMA-7.3 injection visualised by PET imaging compared to histopathology in subjects with PCa, if histopathology information is available.
3. Use of kinetic modelling data to investigate distribution of  $^{18}\text{F}$ -rhPSMA-7.3 in subjects with PCa.
4. Use of kinetic modelling data to optimise the imaging protocol for future studies in subjects with PCa, by estimating *in vivo*  $^{18}\text{F}$  radioactivity in PCa lesions.
5. Analysis of % of radioactive parent compound present in plasma over time in healthy volunteers and subjects with PCa. Relative proportions of radioactive tracer metabolites will be monitored, as well, if detected in significant amounts in the radio-HPLC analysis.

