# 3 STUDY DESIGN

## 3.1 Type and design of the study

This is a phase 1, open-label, single administration, healthy volunteer and patient study of a PET imaging agent performed at a single centre. The use of placebo, randomisation or blinding are not applicable in this study. Altogether 15 evaluable subjects are planned to participate in the trial: 6 healthy volunteer subjects (3 males and 3 females) and 9 patients with PCa (3 in each patient cohort). Additional subjects may be enrolled in order to end up with evaluable PET imaging data from 6 healthy volunteer subjects and 9 patients with PCa. Each subject will receive a single i.v. administration of  $^{18}\text{F}$ -rhPSMA-7.3.

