#### 4.10 Evaluability criteria and additional subjects

Healthy Volunteer Evaluability Criteria:

As it is important that the study has the required number of evaluable healthy volunteers, the following criteria will be applied, and if the healthy volunteer is not evaluable for efficacy, an additional subject may be included in the study to substitute for the non-evaluable subject:

- Completion of scanning sessions I, II and III and collection of venous blood and urine analysis (as described in the Study Imaging Manual) to be able to undertake a calculation of the subject's internal radiation dosimetry.

Patient Evaluability Criteria:

As it is important that each cohort has the required number of evaluable patients, the following criteria will be applied and if the patient is not evaluable for efficacy, an additional subject may be included in the study to substitute for the non-evaluable subject:

- Completion of scanning sessions I and II and collection of venous blood and urine analysis (as described in the Study Imaging Manual) to be able to perform kinetic modelling.
- At least one positive lesion on the F-rhPSMA-7.3 scan.
- Cohort A only: Radical prostatectomy performed within 30 days of the F-rhPSMA-7.3 scan. In case of a delay of the planned surgery by up to 2 days beyond this 30-day window, a subject may still be considered evaluable.

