### 11.2 Source data

Study-specific source data forms will be prepared by CRST before study initiation. Access to the source data revealing the identity of the study subjects is only to study personnel. The generated source data are stored within the ISF at CRST, and are to be archived by CRST according to CRST's SOPs.

TPC will collect, store and handle source data related to IMP handling and dosing, PET/CT imaging and blood and urine radioactivity analysis according to its standard practices, defined

in TPC's SOPs. The imaging-related raw data and the results of the blood and urine radioactivity measurements will not be transcribed into the eCRFs.

The detailed results of the histopathology and immunohistochemistry analysis of the prostate specimens of the Cohort A subjects will be reported separately for each Cohort A subject in a Histopathology and Immunohistochemistry Report to be prepared by the study pathologists and to be included as an Appendix in the Clinical Study Report. These individual pathologist's reports are considered as source data. The histopathology and immunohistochemistry analysis results that are to be entered into the eCRF are listed in section 8.2.6 above. Copies of the pathologists' reports will be entered into the patient records of the Cohort A patients held by Turku University Hospital.

The results of the laboratory blood and urine safety determinations are stored as print-outs within the ISF at CRST and also in electronic form in the patient records of TYKSLAB, Hospital District of Southwest Finland, the personnel of which is bound to professional secrecy. The coded 12-lead ECG print-outs are stored within the ISF at CRST.

The contact information of the subject's next-of-kin will be destroyed before the ISF is archived. Archiving will be performed according to the SOPs of CRST, after database lock.

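### One role, the on-site investigator, both reads the PET and matches PET lesions to histopathology, and the protocol does not require the read to be fixed before Cohort A surgical pathology is known

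*Protocol*

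**What the plan says.** Section 8.2.6 (and the Efficacy Analysis part of the synopsis) states that "the lesion(s) detected on the PET images will be visually evaluated by the on-site investigator". It then says that the assessment of which PET lesion "matches the lesion for which histopathology results are available will be made by the on-site investigator". Both tasks go to the same role.

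Section 3.1 adds: "The use of placebo, randomisation or blinding are not applicable in this study". Section 3.2 repeats that randomisation and blinding do not apply.

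The result feeds secondary endpoint 2 (section 2.4), tracer uptake "visualised by PET imaging compared to histopathology in subjects with PCa, if histopathology information is available". It also feeds the Gleason-versus-uptake comparison in 8.2.6 and lesion detectability in 7.2.3. Section 4.11 makes histopathology the standard of truth for Cohort A.

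On timing, section 4.10 has "Cohort A only: Radical prostatectomy performed within 30 days of the" scan, with a delay of up to 2 further days tolerated. On pathology, section 8.2.6 describes a report for each Cohort A subject "to be prepared by the study pathologist and to be included as an Appendix in the Clinical Study Report". Section 11.2 says: "Copies of the pathologists' reports will be entered into the patient records of the Cohort A patients held by Turku University Hospital".

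**The concern.** Where histology is the reference, the imaging read is informative only if it does not depend on that reference. Here the role that calls the PET lesions also decides which of them corresponds to which carcinoma focus in the specimen. The protocol does not ask that the lesion list exist in fixed form beforehand. A faint region could be called a lesion after the pathology shows a focus there. A region could be redrawn, or a strongly avid lesion paired with the higher-grade focus. None of this needs bad intent.

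What is at stake is the study's only direct PET-to-surgical-specimen evidence. Any error tends to run one way, towards better agreement and a steeper relation between SUV and grade.

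**Working it through.** **1. What the protocol fixes and what it leaves open**

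- Reader: the on-site investigator (8.2.6, synopsis). No second or independent reader is named.
- Matcher: the on-site investigator (8.2.6, synopsis). No anatomical matching rule is given.
- Who derives the SUVs: not stated. Section 8.2.6 says only that they will be derived.
- Who grades the specimen: the study pathologist, in a separate report (8.2.6, 11.2).
- Order: surgery follows the scan (4.10), so a read before pathology is feasible. No section requires it.
- Access: the pathology report goes into the hospital record (11.2). No restriction on the PET reader is stated.
- Record: section 11.2 says "The imaging-related raw data and the results of the blood and urine radioactivity measurements will not be transcribed into the eCRFs". The eCRF audit trail (8.7) therefore does not cover the raw images. The protocol does not say whether the lesion list or derived SUVs are entered.
- Location: the eCRF pathology items in 8.2.6 give location for surgical margins and lymph nodes, but not for carcinoma foci within the prostate.

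**2. How much freedom matching gives (illustration)**

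The protocol states no figure to reproduce here, since section 8.2.2 sets no hypotheses. It gives no lesion counts either, so they are assumed.

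Take the 3 Cohort A patients, each with L lesions on PET and the same L on histology. Let n = 3L, with SUV ranks and grade ranks independent and untied (no true association).

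- Possible within-patient pairings: (L!)³.
- The pairing that agrees best puts both sets in the same order within each patient.
- The expected k-th smallest of L ranks drawn from 1 to n is k(n+1)/(L+1).
- Expected sum of products under best pairing: 3 × Σₖ [k(n+1)/(L+1)]².
- Expected sum under pairing blind to SUV and grade: n × [(n+1)/2]².
- Mean rank correlation = (difference of the two sums) ÷ [n(n²−1)/12].

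Results:

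- L = 1, n = 3: 1 pairing. Sums 3 × 2² = 12 and 3 × 2² = 12. Correlation 0.
- L = 2, n = 6: 2³ = 8 pairings. Sums 3 × [(7/3)² + (14/3)²] = 81.67 and 6 × 3.5² = 73.5. Divisor 6 × 35/12 = 17.5. Correlation 8.17/17.5 = 0.47.
- L = 3, n = 9: 6³ = 216 pairings. Sums 3 × (2.5² + 5² + 7.5²) = 262.5 and 9 × 5² = 225. Divisor 9 × 80/12 = 60. Correlation 37.5/60 = 0.625, or about 0.63.

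A simulation of 4000 data sets under the same assumptions gives about 0.0, 0.47 and 0.63. Pairing blind to SUV and grade gives about 0.0 for every L.

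These are upper bounds, because real lesions have positions that rule out most pairings. The illustration covers matching only. It does not cover adding a lesion or redrawing its region after pathology.

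**The case against.** The strongest reply is that this is an argument from silence about a low-stakes analysis. Read and matching rules might sit in the SAP, the Study Imaging Manual or the Histopathology and Immunohistochemistry Manual, none of which is at hand. The comparison is exploratory, made only as far as possible, and covers three patients. Those patients cannot establish a Gleason-uptake relation whether or not the read is locked.

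The point on stakes stands and limits the weight of the concern. The point on silence stands only in part. The protocol itself chose who reads and who matches. It cites the imaging manual for acquisition and for completion of scanning and sampling, and the histopathology manual for specimen methods. Neither is cited for read timing or matching. The SAP need only be signed before database lock (8.2.1), when every specimen may already have been reported. A rule on order has to be in force before each report is released.

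A reader might infer more than the text supports:

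- *That one person does everything, including taking the SUVs.* The protocol names a role, not an individual, and names nobody for deriving the SUVs.
- *That the bias could never be detected.* PET source data are stored and each specimen has its own report (11.2), so a later re-read blind to pathology is possible. Focus number, diameter and Gleason score enter the eCRF (8.2.6), so the foci seen by the pathologist remain countable.
- *That a matched fraction or detection rate would shift by a stated amount.* The protocol plans no such measure.
- *That the Gleason grades are open to the PET reader's influence.* They are assigned separately by the pathologist.

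**Conclusion.** The concern holds in a limited form. The reading and matching roles coincide, blinding is set aside, and the protocol does not fix the PET read before the Cohort A pathology is known. The standard of truth can therefore inform lesion calling, region placement and matching. The likely direction of bias is upwards, and it matters when a patient has more than one lesion. With one lesion on each side there is only one possible pairing, though region placement stays open.

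The practical size is modest: three patients, descriptive output, no effect on the primary safety endpoint. The correlations of 0.47 and 0.63 rest on assumed lesion counts and unrestricted matching, so they show the ceiling and are not an estimate. The conclusion also assumes that no unseen manual already orders the read before pathology. The change is still worth making, because it costs little and a prospective read cannot be recreated once the report has been seen.

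**What to change.** Add to section 8.2.6 and the synopsis:

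1. For each Cohort A patient, the PET lesion list (location and SUV measures) is completed, signed and dated before the surgical histopathology report is released to the PET reader.
2. Matching uses lesion location only. It works from a PET lesion list and a pathology location map that show neither SUV nor Gleason values. Locking the list is not enough if the matcher then sees both sets of values. Intraprostatic location is taken from the pathologist's report, since the listed eCRF items do not hold it.
3. Unmatched PET lesions and unmatched pathology lesions are both listed.
4. Any later change to the read is kept as a separate, flagged post-pathology read.

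The cost is one dated sign-off per Cohort A patient, recording of lesion location, and later corrections shown separately. No extra reader, visit or procedure is needed.

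The change has limits. It does nothing for the metastatic-lesion comparisons, which use historical Gleason score and PSA. Nor does it remove the reader's knowledge of the pre-scan biopsy: histological confirmation is required of all patients, and Gleason score is among the Cohort A entry criteria.

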#### 8.2.7 Analysis of safety variables

##### Physical Examination results

Physical examination results will be categorically summarised as the number and percentage of subjects according to body system and type, subject group and assessment day.

##### Vital signs

For blood pressure and pulse rate, descriptive statistics of actual values and of change from baseline will be used to summarise by subject group and assessment day.

### ECG (12-Lead) at rest

ECG variables will be summarised according to actual values and change from baseline using summary statistics and will be presented by subject group and assessment time point.

### Safety laboratory values

All haematology, clinical chemistry and coagulation laboratory tests will be summarised using descriptive statistics for actual values and change from baseline and presented by subject group and assessment time point.

### Adverse events

All AEs will be summarised according to time of appearance (screening period and post-administration (=TEAE) AEs separately), following classification of the verbatim terms according to the Medical Dictionary for Regulatory Activities (MedDRA) dictionary. The number and percentage of subjects for all classified events will be presented according to System organ class (SOC) and Preferred term (PT) by subject group and overall.

Separate summaries will be presented for all AEs by subject and also for all AEs according to Seriousness, Severity and Relationship.

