## 2.3 Primary endpoint

Safety is the primary endpoint of the study and it will be assessed from data on the occurrence of one or more treatment-emergent AEs from the time of i.v. administration of  $^{18}\text{F}$ -rhPSMA-7.3 throughout the study period, and changes in serum biochemistry, haematology, coagulation, urinalysis, vital signs, ECG, injection site status, and physical examination findings.

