## 6.2 Study periods

[figure not shown]
### Day 1

Before administration of the IMP administration/PET scan, a brief physical examination is performed, 12-lead ECG and vital signs (body temperature, respiration rate, supine systolic and diastolic BP and HR) and body weight are recorded, and blood and urine samples are collected for clinical laboratory tests. In addition, subjects will be asked about possible AEs which have occurred since consent was obtained and about new medications or changes to concomitant medications. AEs will also be monitored throughout the visit. The results of the physical examination, ECG, vital signs, AEs etc. must be reviewed for eligibility before the subject proceeds for the IMP administration and PET scanning. Healthy volunteers already suffering an AE on the day of the scan will be withdrawn or their IMP administration/PET scan visit will be postponed. Each subject will receive IMP as a single i.v. administration of F-rhPSMA-7.3.

After IMP administration, the healthy volunteer subjects will undergo a series of three CT attenuation-correction scans, each followed by multiple whole-body PET acquisitions. The minimum scanning data to be acquired for each healthy volunteer subject is the initial 1 to 90-min serial whole-body scan, 150 to 178-min mid-scan and the 220 to 248-min late scan, as illustrated in the figure below.

The subjects with PCa will undergo two CT attenuation-correction scans and dynamic PET imaging of the pelvic region (Cohort A; BCR patients in Cohort B; patients with biochemical progression in Cohort C) or the body region with one or more metastases defined as representative target lesions (metastatic patients in Cohort B and radiologically progressive patients in Cohort C) for 45 min, then 15 min break, and then multiple base of skull to mid-thigh PET acquisitions up to 118 min p.i. (see the figure below). The investigator will determine what the representative target lesions are in order to ensure that in the Cohort B and C patients all types of metastases, i.e. lymph node metastases, bone metastases, and soft tissue metastases, are represented on the dynamic images.

Once the scan acquisition is completed, the subject will be monitored for vital signs, ECG and AEs until at least 4 hr after IMP administration.

All procedures during the IMP administration day are presented in Table 2 (healthy volunteer subjects) and Table 3 (subjects with PCa).

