### 7.3.3 Adverse events

AEs will be collected throughout the study from informed consent onwards. During the study visits, the subjects are monitored for AEs and they are asked about AEs with non-leading questions. They are asked to report AEs immediately when they appear outside of the visit schedule. Outside of the visits, the subjects are to contact the study personnel in case of a significant AE, particularly in case of possibly IMP-related AEs. In case of minor AEs, the subjects are to report them on their next visit to the study site or during the scheduled telephone contacts. In case of any illness, the subjects are instructed to seek regular medical care and to inform the study site about their condition and possible changes in their medication as soon as possible.

Definitions of adverse events (AE) and serious adverse events (SAE) and the documentation and reporting of them within this study follow GCP, EU and Finnish national guidance.

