#### Adverse Events

An AE is defined as any untoward medical occurrence experienced by a subject, whether or not considered related to IMP administration by the Investigator. For the current study, all AEs will be coded using the Medical Dictionary for Regulatory Activities (MedDRA, version 21.0 or later) by the data management (DM) provider in co-operation with CRST.

AEs are:

- Unfavourable changes in general condition.
- Subjective or objective signs/symptoms.
- Concomitant diseases or accidents.
- Clinically relevant adverse changes in laboratory parameters observed in a subject in the course of a clinical study.

AEs comprise all disturbances of general health status, subjective and objective disease symptoms (including significant, clinically relevant laboratory abnormalities), concomitant diseases, and accidents observed in the context of a clinical trial, irrespective of a possible causal relationship with IMP administration.

All AEs, whether volunteered, elicited, or noted on physical examination, will be recorded throughout the study, i.e., from the screening visit until the end of the subject's participation. AEs that occur prior to IMP administration will be reported separately from treatment-emergent AEs, which will be of particular interest.

When an AE occurs, the first decision will be to determine its severity and relationship to the IMP.

The severity of AEs will be categorised as follows:

- Mild = Experience is minor and does not cause significant discomfort to subject or change in activities of daily living (ADL) compared to subject baseline; subject is aware of symptoms but symptoms are easily tolerated.
- Moderate = Experience is an inconvenience or concern to the subject and causes interference with ADL compared to subject baseline but the subject is able to continue with ADL.
- Severe = Experience significantly interferes with ADL and the subject is incapacitated and/or unable to continue with ADL compared to subject's baseline.

The relationship of an AE to IMP administration will be categorised as follows:

- Related; when there is a reasonable possibility of a causal relationship between IMP administration and an AE (i.e. adverse drug reaction, ADR)
- Not related; when an AE does not follow a reasonable temporal sequence from IMP administration or when an AE can be reasonably explained by other factors including underlying disease, concomitant drugs or concurrent treatment.

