- Not applicable: IMP not administered or AE is prior to IMP administration.

The Investigator or his delegate marks on the AE-CRF all AEs, indicating the Investigator's assessment of a causal relationship to IMP administration using the categories above.

As far as possible, each AE will also be described by its duration (start and end date and time), the actions taken, and, as relevant, the outcome.

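### The TEAE and causality rules do not cover a patient's AE that begins between consent and injection and worsens after injection

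*Protocol*

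**What the plan says.** The primary endpoint (section 2.3) is safety. Its first-named component is the "occurrence of one or more treatment-emergent AEs from the time of i.v. administration of" the tracer. It also takes in "changes in serum biochemistry, haematology, coagulation, urinalysis, vital signs, ECG, injection site status, and physical examination findings".

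AE collection starts before dosing. Section 7.3.3 states: "AEs will be collected throughout the study from informed consent onwards". Screening may start up to 21 days before the IMP (section 6.1).

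The split between TEAEs and other AEs is given twice. Section 7.3.3 says "AEs that occur prior to IMP administration will be reported separately from treatment-emergent AEs, which will be of particular interest". Section 8.2.7 says "All AEs will be summarised according to time of appearance (screening period and post-administration (=TEAE) AEs separately").

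The relationship scale in section 7.3.3 has three categories: related, not related, and a third worded "Not applicable: IMP not administered or AE is prior to IMP administration".

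One rule deals with an AE already present on the day of injection, and it covers one population only. Section 6.2 says: "Healthy volunteers already suffering an AE on the day of the scan will be withdrawn or their IMP administration/PET scan visit will be postponed". For patients, section 6.2 requires AEs, among other findings, to be reviewed for eligibility before injection, but states no equivalent rule.

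**The concern.** The usual reason for a treatment-emergent category is to separate what the product may have caused or aggravated from what was already there. Here the only stated criterion is when the AE appears. An AE that is mild at injection and severe some hours later began before injection. By date of appearance it belongs with the screening-period events, and by the relationship scale it is *Not applicable*. If the investigator keeps one record for the event, it is neither treatment-emergent nor assessed for relatedness, and it drops out of the TEAE table and of any meaningful summary by relationship.

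The two halves of the gap differ in kind. Which table an event goes into can be settled at analysis. Causality and the time of worsening are collected at the site. If the record holds one start time and *Not applicable*, no later analysis rule can recover the judgement that was not made.

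Compared with a definition that includes worsening, an onset-only definition can move the TEAE count in one direction only, downwards.

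**Working it through.** The protocol gives no figure to reproduce: section 8.2.2 states no hypothesis, and there is no assumed TEAE rate. The check is a reading of the AE rules against one case, followed by arithmetic for scale.

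**Tracing the case.** A patient consents, develops an AE before injection, still has it on Day 1, passes the Day 1 review, is injected, and the AE becomes more severe.

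1. *Is it collected as an AE?* Yes. Collection runs from consent (7.3.3). A condition already present at consent would instead be medical history (7.1.1), so this trap does not catch it. The exposed window is consent to injection, with screening starting at most 21 days before the IMP.
2. *Can the subject be injected with it?* A healthy volunteer, not that day (6.2). A patient, possibly, subject to the eligibility review.
3. *Is it a TEAE under 8.2.7?* By time of appearance under its existing record, no. If the worsening is entered as a separate AE after injection, yes.
4. *Does the protocol require a separate entry?* No. The AE definition in 7.3.3 is wide enough to admit a deterioration as an AE, but nothing says a change in severity opens a new record. Each AE is described by a start and an end.
5. *Is causality assessed?* Under the existing record the category is *Not applicable*. Under a new post-dose entry it would be related or not related.
6. *Is it visible elsewhere in the primary endpoint?* If it shows in laboratory values, vital signs, ECG, injection site or examination, it can appear in those summaries. A purely symptomatic worsening may not.

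Steps 3 to 5 depend on a recording choice that the protocol leaves open.

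**Scale.** Inputs are the planned evaluable numbers from section 8.1: 9 patients, 3 per cohort, 15 subjects in all. One uncounted subject shifts the percentage by 100/n:

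- one cohort: 100/3 = 33.3 points
- all patients: 100/9 = 11.1 points
- all subjects: 100/15 = 6.7 points

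Safety is analysed in everyone dosed (8.2.3), and non-evaluable subjects may be supplemented (4.10), so the actual denominators may be larger and the shifts smaller.

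If no patient had any other TEAE, the result would read 0/9 and not 1/9. For scale only, since the protocol does not specify confidence intervals, the exact two-sided 95 % limits are:

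- 0/9: 0 to 1 − 0.025^(1/9) = 33.6 %
- 1/9 = 11.1 %: 0.3 to 48.2 %

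**Frequency.** The protocol gives none. If each patient had probability p of such an event (an assumption), the chance of at least one among 9 is 1 − (1 − p)^9:

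- p = 2 %: 16.6 %
- p = 5 %: 37.0 %
- p = 10 %: 61.3 %
- p = 20 %: 86.6 %

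The range only shows that the answer depends on p, which is unknown.

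**The case against.** The strongest reply is that this is detail for the SAP. Section 8.2 describes itself as a summary, section 8.2.1 defers detail to a SAP that is not at hand, and a worsening clause is commonly placed there. That would be a full answer if the protocol were merely silent. It is not: section 8.2.7 equates post-administration AEs with TEAEs, and section 7.3.3 fixes a causality category for pre-dose AEs. A SAP could widen the TEAE definition, but it could not supply a causality assessment or a time of worsening that the site never recorded.

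A second reply is that the AE definition already admits a worsening as a new AE, with its own start time and causality. This is correct and it limits the point. A reader might infer that worsening events are excluded from the primary endpoint, or that they are forced to *Not applicable*. The text does not go that far. Section 8.2.7 speaks of time of appearance, not of first appearance, and no sentence excludes a worsening. What stands is that a new entry is permitted and not required, so identical events could be classified differently.

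A third reply is that the primary endpoint is wider than TEAEs and that subject listings are planned (8.2.4). In a study this small, a worsening with a measurable sign would probably be seen. That also stands, and it confines the loss mainly to symptoms such as pain, fatigue or nausea.

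A fourth reply is that 1/3, 1/9 and 1/15 are the effect of any single event and do not measure this rule. That is fair: they show what one misclassified patient would do, not how likely one is. Nor do the documents support a claim that such AEs are common in these patients, since symptoms already present at consent are medical history.

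**Conclusion.** The point holds in a limited form. In patients with prostate cancer, an AE that starts between consent and injection and worsens afterwards under the same record need not be counted as a TEAE and receives no relatedness assessment. Any effect lowers the TEAE component of the primary endpoint, mainly through symptomatic worsening.

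One such patient is worth 11.1 points among 9 patients or 33.3 points in a cohort of 3, using planned evaluable numbers. The number of such patients cannot be estimated from the protocol and may be zero. The study is exploratory and descriptive, so no decision rule turns on the count.

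The conclusion assumes that the site follows the wording literally and that no eCRF completion instruction outside the protocol already requires a new entry for worsening. It does not support the stronger inference that the plan removes worsening events from the primary endpoint. It is still worth correcting, because the change is small and the causality half has to be settled before the data are recorded.

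**What to change.** In section 8.2.7, define a TEAE as any AE with onset after the start of IMP administration, or any AE present before it that worsens in severity or seriousness afterwards.

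In section 7.3.3, require such a worsening to be recorded as a new AE with its own start time, severity and causality. Limit *Not applicable* to AEs where no IMP was given, or that began before the IMP and did not worsen after it. The sentence there that reports pre-dose AEs separately ("AEs that occur prior to IMP administration will be reported separately from treatment-emergent AEs") can stay once it is read with the amended definition.

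The cost is about two sentences and one eCRF completion instruction. Design, sample size and clinical management are unchanged. The downside is that the TEAE count may come out slightly less favourable.
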